10.1.2 Causality Classification

Only those adverse events considered to be related to product will be collected.

RAEs are reports including good reasons and sufficient information (e.g. plausible time sequence, dose-response relationship, pharmacology, positive de-challenge and/or re-challenge) to assume a causal relationship with the Survey medication in the sense that it is plausible, conceivable or likely.

10.1.3 Assessment of expectedness

The expectedness of an RAE/reaction shall be determined by the Sponsor according to the Investigator's Brochure for an unapproved Survey medication or Summary of Product Characteristics (SmPC) or Package Insert for an authorised medicinal product which is being used according to the terms and conditions of the marketing authorisation.

The reference document for assessing expectedness of RAEs/reactions in this survey will be: Summary of Product Characteristics, Czech Republic, Last approved version dated 30.06.2008, ref.nr.6324/2007;24731/2008;35386/2008).

10.1.4 Laboratory Test Abnormalities

NA

10.1.5 Abnormal Physical Examination Findings

NA

10.1.6 Other Investigation Abnormal Findings

NA

10.2 Recording and Follow-up of related adverse events

At each visit the subject should be asked a non-leading question such as: "Do you feel different in any way since starting the new treatment/the last assessment?"

All AEs related to survey medication will be recorded on the RAE page(s) of the CRF. Related Events involving drug reactions, accidents, illnesses with onset during the treatment phase of the survey, or exacerbation's of pre-existing illnesses should be recorded.

RAEs already recorded and designated as 'continuing' should be reviewed at each subsequent assessment.

For all registered RAEs, the Investigator must pursue and obtain information adequate both to determine the outcome of the RAE and to assess whether it meets the criteria for classification as a RSAE requiring immediate notification to the Sponsor or its designated representative. The Investigator is required to assess causality and record that assessment on the CRF. Follow-up of the RAE, after the date of therapy discontinuation, is required if the RAE or its sequel persist. Follow-up is required until the event or its sequel resolve or stabilise at a level acceptable to the Investigator and the Sponsor's clinical monitor or his/her designated representative.

10.3 Related Serious adverse events

10.3.1 Definitions

All related to survey medication SAEs (as defined below) must be reported immediately (within 24 hours of the Investigator's knowledge of the event) to the pharmacovigilance contact specified at the beginning of this protocol. If the immediate report is submitted by telephone, this must be followed by detailed written reports using the Spontaneous report form.

A Related SAE is any RAE occurring at any dose that:

1. results in death;
2. is life threatening, that is any event that places the subject at immediate risk of death from the reaction as it occurred. It does not include a reaction that, had it occurred in a more severe form, might have caused death;
3. results in in-patient hospitalisation or prolongation of existing hospitalisation, excluding admission for social or administrative reasons (see further);
4. results in a persistent or significant disability/incapacity, where disability is a substantial disruption of a person's ability to conduct normal life functions;
5. results in congenital anomaly/birth defect in the offspring of a subject who received the Survey medication;
6. is an important medical event that may not result in death, be life-threatening, or require hospitalisation when, based upon appropriate medical judgement, may jeopardise the subject and may require medical or surgical intervention to prevent one of the outcomes listed in this definition. Examples of such medical events include allergic bronchospasm requiring intensive treatment in an emergency room or at home, blood dyscrasias or convulsions that do not result in in-patient hospitalisation, or the development of drug dependency or drug abuse.

Regardless of the above criteria, any additional related AE that the Sponsor or an Investigator considers serious should be immediately reported to the Sponsor and included in the corporate related SAEs database system.

- **Hospitalisation** is defined as any in-patient admission (even if less than 24 hours). For chronic or long-term in-patients, in-patient admission also includes transfer within the hospital to an acute/intensive care in-patient unit.
- **Prolongation of hospitalisation** is defined as any extension of an in-patient hospitalisation beyond the stay anticipated/required in relation to the original reason for the initial admission, **as determined by the Investigator or treating physician**. For protocol-specified hospitalisation in clinical trials, prolongation is defined as any extension beyond the length of stay described in the protocol. Prolongation in the absence of a precipitating, treatment-emergent, clinical RAE (i.e., not associated with the development of a new RAE or worsening of a pre-existing condition) may meet criteria for "seriousness" but is not an adverse experience and thus is not subject to immediate reporting to the Sponsor.
- Pre-planned or elective treatments/surgical procedures should be noted in the patient's screening documentation. Hospitalisation for a pre-planned or elective

treatment/surgical procedure should not be reported as an related SAE unless there are complications or sequel which meet the criteria for seriousness described above.

10.3.2 Reporting Requirments

In this Post Marketing Survey the collection of adverse events should be limited to related serious and related non-serious events . All related serious and related non serious adverse events will be reported by Investigator to Sponsor on the Spontaneous Adverse Event Report Form . Serious Adverse Events will be reported immediately (within 24 hours) by the investigator to the sponsor using the Spontaneous Adverse Reporting Form .

10.3.3 Mandatory Information for Reporting related SAE

The following information is the minimum that must be provided to the Sponsor pharmacovigilance contact within 24 hours for each related SAE:

- Trial number
- Centre number
- Subject number
- related AE
- Investigator's name and contact details

The additional information included in the related SAE form must be provided to the Sponsor or representative as soon as it is available. Upon receipt of the initial report, the Sponsor will ask for the Investigator's causality assessment if it was not provided with the initial report.

The Investigator should report a diagnosis or a syndrome rather than individual signs or symptoms. The Investigator should also try to separate a primary RAE considered as the foremost untoward medical occurrence from secondary RAEs which occurred as complications.

10.4 Pregnancy

NA

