Study Design:	Centres will prescribe Dysport according to their usual practice and within the latest approved Summary of Product Characteristics (SmPC). (Last approved version dated 30.06.2008, ref.nr.6324/2007;24731/2008;35386/2008). Each center will record the treated muscles and the dose of Dysport administered. At visits during following year (5 visits assumed) prescriber will evaluate treatment success and administration interval and fulfil simple Case Record Form (CRF). Based on the subject interview, the prescriber will fulfil the DAS QOL questionnaire and in case of related AE, the AE reporting forms. Both will be returned to Ipsen.
Study duration	“Recruitment” period will be 18 months. Duration of Study is approximately one year per subject (three injections expected within 1 year according to SmPC)
Study Population:	Reports on up to 200 male or female adult subjects will be collected. Study Inclusion Criteria All subjects must fulfil the following: 
 • Subjects with stroke either haemorrhagical or ischemic origin and stroke onset at least 3 months prior to study entry scheduled to receive Dysport. • Adults over the age of 18 years • Arm spasticity with Modified Ashworth scale ≥ 2 at least in one part Study Exclusion Criteria Subjects presenting with any of the following will not be included in the Study: 
 • Hypersensitivity to any Dysport ingredient • Pregnancy • Previous administration of botulinum toxin

Study Treatment:	
Investigational Medicinal Product (IMP):
 
Dysport, botulinum toxin A, presented in a form of lyophilizate injections is used for several indications including post stroke arm spasticity of adults. The pack contains 1 or 2 glass vials with lyophilizate and should be reconstituted with 0,9 % NaCl before administration.
 
The dosage will be set by physician according to SmPC. The maximal dose will be 1000 U per session.

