4. STUDY DESIGN

4.1 Overview

Centres will prescribe Dysport according to their usual practice and within the Summary of Product Characteristics (SmPC). Latest approved version ref.nr. 6324/2007,24731/2008,35386/2008 is dated 30.06.2008. Each center will record the treated muscles and the dose of Dysport administered. Before the first administration and 4 weeks after that, prescriber will evaluate treatment success and will assess quality of life in the range of routine practice (if available). According to SmPC, 3 Dysport injections are expected within 1 year. During all visits performed

within a year, simple Case Record Form (CRF) will be fulfilled. In case of treatment related AE, the AE reporting forms will be fulfilled. Both will be returned to Ipsen.

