6.3 Exclusion Criteria

Subjects will not be included in the Study if :

- 1) Subject has hypersensitivity to Dysport (any of its components) or drugs with a similar chemical structure.
- 2) Subject is pregnant. Absence of pregnancy should be confirmed prior injecting the product.
- 3) Subject has been previously treated with any botulinum toxin.

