7.2 Study Visits

7.2.1 Baseline (Day 1, visit V1)

All subjects attending the centre for their normal Dysport treatment will receive Dysport as decided by the treating physician, in accordance with the SmPC. The following details will be recorded on the Study CRF:

- Centre number, Subject number, Subject initials
- Demography
- Significant medical or surgical history
- Prior and concomitant medication
- Previous medication for stroke
- Stroke details
- Modified Ashworth scale, DAS scale
- Dysport administration (location, dosage)
- Related Adverse Events (at this visit injection related AEs only)

7.2.2 *Follow-up visits (V2, V3, V4, V5)*

At the subject's scheduled return to the center (Visit 2, the date depends on investigator's judgement, it is usually about 4 weeks later), the investigator will make routine control of treatment efficacy (V2). During this visit, both Modified Ashworth and DAS scales are evaluated according to routine practice. Treating physician will also perform an assessment of safety, and details on any treatment related adverse events will be collected.

After fadeaway of Dysport effect, subject will come to next injection visits (V3, V4,) within which Dysport will be injected again according to investigator decision. Treatment interval will be counted (V3 - V1, V4 - V3).

Visit V5 will be performed by telephone contact and is also the End of study visit.

During visit 5, which will take place within 3-5 weeks following last injection, subjects will be contacted by telephone to discuss any treatment related Adverse events (RAEs) that they have had since their treatment and Modified Asworth and DAS scale.

Collection of treatment related adverse events, if any, will be made during V1, V2, V3, V4 and V5.

7.2.3 *Study Completion or Withdrawal*

Study is completed if current visits exceed 1 year from visit 1 or when the Dysport treatment is finished/withdrawn

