8.2 Safety Endpoints and Evaluations

8.2.1 Related Adverse Events

Treatment related AEs will be collected from the first treatment administration to the end of the Study. RAEs will be elicited by spontaneous reports. Due to the non-interventional character of the study, no pro-active safety data collection should take place and only spontaneously mentioned safety events should be reported. Further details for RAE reporting can be found in Section 10.

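### Section 10.4 sets pregnancy aside as not applicable, so no passage requires an exposed pregnancy to be reported, and a birth would usually fall after the subject's collection window

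*Protocol*

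**What the plan says.** - Section 10.4 consists of its title and two letters: "10.4 Pregnancy NA".
- The synopsis admits both sexes: "Reports on up to 200 male or female adult subjects will be collected". Neither it nor section 6.2 states an upper age limit or a criterion on childbearing potential.
- Section 6.3 lists pregnancy as an exclusion: "Subject is pregnant. Absence of pregnancy should be confirmed prior injecting the product". Table 1 in section 7.1 places eligibility at V1 only and has no row for a pregnancy check. It places injections at V1, V3 and V4.
- Section 4.1: "According to SmPC, 3 Dysport injections are expected within 1 year".
- Section 10.3.1 gives six criteria that make a related adverse event serious. Item 5 applies when the event "results in congenital anomaly/birth defect in the offspring of a subject who received the Survey medication".
- Section 8.2.1 sets the period: "Treatment related AEs will be collected from the first treatment administration to the end of the Study". It also rules out pro-active collection of safety data. Sections 10, 10.1.2 and 10.3.2 restrict collection to events judged related to the product.
- Section 7.2.2 fixes the last contact: "During visit 5, which will take place within 3-5 weeks following last injection", by telephone. Section 7.2.3 also ends a subject's study when treatment is finished or withdrawn.
- Section 10.2 requires follow-up after therapy only for a related event that persists. Section 10.5 sets a limit counted from the last dose (28 days), but for deaths only.

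**The concern.** Three parts of the protocol treat pregnancy as something that can arise: the eligibility criteria, the seriousness criteria, and the enrolment of women for repeated injection. The section meant to say what to do about it says that it does not apply. A woman who conceives after V1 and is injected before or during that pregnancy has an exposed pregnancy. An uncomplicated pregnancy is not an unwanted condition judged causally related to the product, so it does not meet the section 10 definition of a reportable event. A site that follows the text need not report it, and NA may be read as advice not to.

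The primary objective in section 3.1 is a further assessment of the risk and benefit of a marketed product. If the report shows no events under item 5, a reader may take that as reassurance, although the plan had little means of seeing one. The sponsor's pharmacovigilance contact may also not hear of an exposure whose outcome it could have followed. No efficacy summary is affected.

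**Working it through.** The plan gives no figure to reproduce: section 11.3 chooses 200 subjects on practical grounds and section 11.3.1 excludes testing. The check is date arithmetic.

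**From the protocol.** Injections at V1 (day 1), V3 and V4. V5 is 21 to 35 days after V4. Duration is about one year per subject.

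**Assumptions, not in the protocol.** Conception to term birth takes g = 266 days (range 259-280). The two injection intervals are equal, of length i, between 12 and 24 weeks. Section 7.2.2 ties V3 and V4 to the fading of effect and fixes no interval.

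**Formulas.** V4 = 1 + 2i. V5 = V4 + 21 to V4 + 35. Birth day = conception day + g. Latest conception day with a term birth by V5 = V5 - g.

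**Conception at V4.** Birth follows V5 by g - 35 to g - 21 days: 266 - 35 = 231 and 266 - 21 = 245. Over the range of g this is 224 to 259 days. The interval i does not matter here.

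**Conception on day 1.** Birth is at day 1 + 266 = 267.

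| Interval (weeks) | V4 (day) | V5 (day) | Latest conception day with term birth by V5 |
|---|---|---|---|
| 12 | 169 | 190-204 | none |
| 14 | 197 | 218-232 | none |
| 16 | 225 | 246-260 | none |
| 17.33 (52/3) | 244 | 265-279 | none to 13 |
| 20 | 281 | 302-316 | 36-50 |
| 24 | 337 | 358-372 | 92-106 |

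A day-1 conception delivers by V5 only if 2i + 35 or 2i + 21 reaches 266. That gives i = (266 - 35)/2 = 115.5 days = 16.5 weeks, or (266 - 21)/2 = 122.5 days = 17.5 weeks.

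**Full 365-day window.** Latest conception day is 365 - 266 = 99, and 99/365 = 27%. Over the range of g it is 365 - 280 = 85 (23%) to 365 - 259 = 106 (29%).

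**Early end.** If treatment is stopped once a pregnancy is recognised, section 7.2.3 completes the subject's study at that point, before a term birth.

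**Number of women.** The protocol gives none. For scale only, if 2-5% of 200 subjects were women of childbearing potential (assumption), that is 0.02 × 200 = 4 to 0.05 × 200 = 10 women. The expected number of pregnancies cannot be computed from the document.

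**The case against.** The strongest reply is that nothing here is a strict contradiction. Item 5 belongs to a generic list that classifies events already judged related; it is not an endpoint. Section 4.2.2 names only the collection of related adverse events. NA in 10.4 can be read as meaning that there is no separate pregnancy procedure, and a related birth defect that the investigator learns of would still go to the sponsor within 24 hours under 10.3.1 and 10.3.2. That stands. The sections can all be obeyed at once; what they leave is a gap.

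A reader might infer that a birth defect could never be seen and that ascertainment is zero. The documents do not support that. Intervals are not fixed, and with long ones or a full-year window an early conception can reach term in time. A preterm birth or a defect found before birth could also fall inside. Section 4.3.1 moreover defines the Study as running from first inclusion to the last V5, after 18 months of recruitment. If the end of the Study in 8.2.1 is read that way, early subjects have a longer nominal window. Section 7.2.2, which calls V5 the end-of-study visit, supports the per-subject reading. On either reading no contact with the subject is planned after her own V5.

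Other safeguards exist. The open question at each visit in section 10.2 may bring a pregnancy to light, and local regulatory requirements apply (sections 5.1 and 10.7). The entry exclusion lowers the chance of exposure. None of these passages states a duty to report a pregnancy. Section 6.3 asks that "Absence of pregnancy should be confirmed prior injecting the product" without limiting this to the first injection. Even a check at every injection would not cover conception afterwards.

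Finally, sections 4.3 and 8.2.1 keep collection passive, and section 11.3 disclaims definitive safety conclusions. This limits the weight of the point. It does not rule out reporting a pregnancy that has become known.

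**Conclusion.** The point holds as an inconsistency and a capture gap. Section 10.4 does not fit with section 6.3 or with item 5 of section 10.3.1. As written, an exposed pregnancy that is not itself a related event need not be reported, and its outcome would usually fall after the subject's last contact. At 266 days to term, the shortfall for conception at V4 is 231-245 days. With equal intervals up to 16 weeks, no conception after V1 reaches term by V5. At best, roughly the first 23-29% of a full one-year window is covered, if the subject remains in the study. These figures rest on the assumed gestation and intervals.

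The inference that the study would show no birth defects whatever happened goes too far, for the reasons given above. What is supported is that a zero count under item 5 would say little. The number of women affected is unknown and probably small, and no estimate, test or sample size changes. It is a modest point that is cheap to put right.

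**What to change.** Replace NA in section 10.4 with an instruction along these lines: any pregnancy that becomes known to the investigator between the first injection and the end-of-study contact is reported to the sponsor's pharmacovigilance contact on the Spontaneous Adverse Event Report Form, whether or not an adverse event has occurred, and its outcome is passed on when known, even after that contact. State in sections 8.2.1 and 10.3.2 that this is an exception to the related-event and end-of-study limits. Because it covers only pregnancies that become known, it needs no active questioning and respects the passive design.

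Separately, reconcile section 6.3 with Table 1 in section 7.1 on which injections the pregnancy check refers to. The clinical rule itself is for the sponsor to decide.

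The cost is a short protocol amendment, use of a form that already exists, and a small reporting workload outside the visit schedule for what is probably a handful of subjects at most.

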10.5 Deaths

All related AEs resulting in death either during the survey period or within 28 days after the last dose of Survey medication, must be reported as an related SAE within 24 hours of the Investigator's knowledge of the event.

The convention for recording death is as follows:

- RAE term: lead cause of death (e.g. multiple organ failure, pneumonia, myocardial infarction).
- Outcome: fatal.
- The **only exception** is if the cause of death is unknown (i.e. sudden or unexplained death), in which case the RAE term may be 'Death' or 'Sudden death'.

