7. METHODOLOGY

7.1 STUDY Schedule

The schedule of observations and assessments during the Study are summarised below.

Table 1. Schedule of Observations

	V1 (D1)	V2 (approx. D28)	V 3	V 4	V5 - phone contact approx 3-5 weeks after V4
Demography& Eligibility	X				
Significant medical or surgical history	X				
Prior and concomitant medications	X				
Previous medication for stroke	X				
Treatment injections	X		X	X	
Related Adverse events	X	X	X	X	X
Modified Asworth assessment	X	X	Optional	Optional	X
DAS assessment	X	X	Optional	Optional	X
Interval assessment			X	X	

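### Planned contact after the last dose is not guaranteed to reach the end of the 28-day window that 10.5 sets for fatal related events: the closing call may be made at day 21, and 7.2.3 can complete a subject before the call

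*Protocol*

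**What the plan says.** Section 10.5 of the protocol defines the reportable fatal events as "All related AEs resulting in death either during the survey period or within 28 days after the last dose of Survey medication". Such events "must be reported as an related SAE within 24 hours of the Investigator's knowledge of the event".

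The last planned contact is V5. The table in 7.1 labels it "V5 - phone contact approx 3-5 weeks after V4". The text of 7.2.2 uses a different anchor: "During visit 5, which will take place within 3-5 weeks following last injection". The same section states "Visit V5 will be performed by telephone contact and is also the End of study visit", and lists V1 to V5 as the occasions on which RAEs are collected.

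On the length of collection, 8.2.1 says "Treatment related AEs will be collected from the first treatment administration to the end of the Study". Section 10 bounds the definition of an RAE in the same way.

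Section 7.2.3 gives two ways in which a subject completes. The first is "Study is completed if current visits exceed 1 year from visit 1". The second is that Dysport treatment has ended or been withdrawn. Neither mentions V5.

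**The concern.** The protocol states a post-dose period over which fatal related events matter, but does not tie its last contact to the end of that period. A site that follows the visit schedule exactly can close a subject a week early. Under the second limb of 7.2.3, read literally, it can close the subject on the day of the last dose.

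The contact matters because this study has little other means of learning of an event. Section 8.2.1 rules out pro-active safety collection, and 10.2 relies on a non-leading question put at each visit. After V5 there is no further visit. Section 10.2 extends follow-up only for RAEs already recorded that persist; it does not look for new ones.

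At stake is the completeness of the only safety endpoint (4.2.2) in a study whose primary objective is risk and benefit (3.1), over the stretch after the last dose that the protocol itself singles out.

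**Working it through.** This is day arithmetic; no power or sample-size figure is involved.

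**Inputs**
- Window for fatal related events: 28 days after the last dose (10.5).
- V5: 3 to 5 weeks after the last injection (7.2.2), or approximately that after V4 (7.1).
- Completion: one year from V1, or end or withdrawal of treatment (7.2.3).
- Expected pace: three injections in a year (4.1, 4.3.1), given at V1, V3 and V4 (7.1).

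**1. The call window against the 28 days**
- 3 × 7 = day 21; 5 × 7 = day 35. Permitted whole days: 35 − 21 + 1 = 15.
- Days without planned contact = max(0, 28 − call day). Call on day 21: 7. Day 24: 4. Day 27: 1. Days 28 to 35: 0.
- Worst in-window case: 7/28 = 25% of the window.
- Call days that fall short: 21 to 27, which is 7 of 15. The other 8 cover the window in full.
- If calls were spread evenly over the 15 days (an assumption; the protocol gives no distribution), the mean shortfall would be (7 + 6 + 5 + 4 + 3 + 2 + 1)/15 = 28/15 = 1.9 days per subject.

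**2. The completion rule, treatment-ended limb**
- If a subject completes when treatment ends, and that is dated to the last injection, planned post-dose observation is 0 of 28 days. This conflicts with 7.2.2, which makes V5 the end-of-study visit.

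**3. The completion rule, one-year limb**
- It falls before post-dose day 28 only if V4 is later than 365 − 28 = 337 days after V1, and before the earliest V5 only if V4 is later than 365 − 21 = 344 days after V1.
- At the protocol's pace, intervals are 365/3 ≈ 122 days, so V4 falls at about 2 × 365/3 ≈ day 243, leaving about 122 days.
- With assumed intervals of 12 to 16 weeks, V4 falls 168 to 224 days after V1, leaving 197 to 141 days.
- Reaching day 337 needs a mean interval of 337/2 = 168.5 days, about 24 weeks. This limb would seldom apply.

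**4. The anchor**
- The table counts V5 from V4; the text counts from the last injection. For a subject whose last injection is at V1 or V3, the table gives no date for V5. After a single injection, V2 at about day 28 may serve as a contact, but its date is left to the investigator. After a last injection at V3, only the wording of 7.2.2 supplies a call.

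**5. What is collected after an early call**
- Fatal related events: still reportable under 10.5, once known.
- New non-fatal RAEs: 7.2.2 confines collection to V1 to V5, and 8.2.1 ends it with the study. If the end of the study in 8.2.1 meant the last subject's V5 (4.3.1), collection would nominally run on, but still with no visit at which to ask.

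**The case against.** The strongest reply is that 10.5 contradicts nothing. It covers deaths "either during the survey period or within 28 days after the last dose of Survey medication", so it expressly reaches past the survey period, and the investigator's knowledge triggers it, not a visit. A passive duty may outlast the last contact. **This stands:** a related death on day 25 after a day-21 call is still reportable. What the reply does not supply is a route by which the investigator would learn of it.

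Second, the 28 days apply to fatal related events only; the protocol sets no such window for other RAEs. **This stands.** The loss of non-fatal RAEs follows from ending collection at V5 and is not a breach of 10.5.

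Third, the study is descriptive, disclaims definitive safety conclusions (11.3) and adds no safety measures beyond normal practice (4.3). **This stands** as a limit on importance. It does not weigh against the remedy, which moves a call already planned.

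Two stronger readings are tempting. A reader might infer that the post-dose window is not observed at all. The documents do not support that: a call on days 28 to 35 covers it fully, and the earliest in-window call misses only its last 7 days. A reader might also infer that risk under repeated treatment is understated, because earlier injections are followed to the next visit and the last for only 21 to 35 days. The follow-up does differ, but nothing in the protocol shows that related events arise late after an injection or become more frequent with repetition, so neither a direction nor an amount is shown. How RAEs are tabulated by injection belongs to the separate Reporting and Analysis Plan (11.4).

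**Conclusion.** The point holds as a modest misalignment. Planned contact after the last dose is not guaranteed to reach day 28. With an in-window call the shortfall is at most 7 of 28 days (25%) and arises on 7 of the 15 permitted call days. It can be the whole window if 7.2.3 is applied literally when treatment ends.

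Of the two limbs of 7.2.3, the treatment-ended limb is the real conflict. The one-year limb matters only if the last injection falls after about day 337, against about day 243 at the protocol's expected pace, and its wording about visits need not be a calendar cut-off.

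The 7 days rest on taking 3 weeks as day 21; the table's approximate wording could allow a slightly earlier call. The 0-day case rests on the literal reading of 7.2.3. How many subjects would be affected cannot be derived from the protocol.

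**What to change.** Reconcile 7.1, 7.2.2, 7.2.3, 8.2.1 and 10.5, taking the protocol's 28 days as given:
- In 7.1 and 7.2.2, anchor V5 to the last injection actually given, and make the call no earlier than day 28, within the existing upper limit of 5 weeks.
- In 7.2.3, state that neither limb completes a subject before that call.
- In 8.2.1, state that RAE collection for a subject runs to that call, so that it covers the period named in 10.5.

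The cost is small. The call already exists and days 28 to 35 are already permitted, so no visit or procedure is added and the study stays non-interventional. The sites' call window narrows from 15 days to 8, and an occasional subject closes shortly after one year. A subject who refuses further contact would still be unobserved; that can be recorded with the discontinuation reason under 6.4.
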